3.12. Health Outcomes

The PRO questionnaires will be analyzed using the EAS, unless specified otherwise.

Item-level missingness is dealt with as per the instrument developers' instruction.

Additional psychometric analyses will be performed post-hoc by Value, Evidence, and Outcomes at Lilly and documented in a separate analysis plan.

3.12.1. Patient Global Impression of Severity (PGIS)

The counts and percentages of participants endorsing each PGIS response category at each time point will be summarized by nominal visit and by treatment. A shift table from baseline to postbaseline of the 5 PGIS response categories at each postbaseline visit by treatment will be created.

3.12.2. Chronic Liver Disease Questionnaire for Nonalcoholic Fatty Liver Disease (CLDQ-NAFLD)

The following parameters will be included from the CLDQ-NAFLD:

- Abdominal domain (3 items; Items 1, 5, 17)
- Activity domain (5 items; Items 7, 9, 14, 30, 31)
- Emotion domain (9 items; Items 10, 12, 15, 16, 19, 20, 24, 26, 34)
- Fatigue domain (6 items; Items 2, 4, 8, 11, 13, 35)
- Systemic domain (6 items; Items 3, 6, 21, 23, 27, 36)
- Worry domain (7 items; Items 18, 22, 25, 28, 29, 32, 33)
- Total score

Individual items are rated on a 7-point scale ranging from “1- All of the time” to “7- None of the time.” Scores are calculated separately for each domain by taking the average of the domain’s items. The total score is calculated by taking the average of the domain scores. Higher scores reflect better health. In the case of missing values, domains scores can be calculated when at least 50% of the items are completed, and the total score should include at least 4 domains.

3.12.3. PROMIS Short Form Fatigue 8a v1.0

The counts and percentages of participants endorsing each response category for each item of the PROMIS Short Form Fatigue 8a v1.0 at each time point will be summarized for each nominal visit and by treatment. Individual item scores are totaled to obtain a raw score, with higher scores indicating more interference. Raw scores can be converted to a T-score.

3.12.4. PROMIS Short Form Pain Interference 4a v1.0

The counts and percentages of participants endorsing each response category for each item of the PROMIS Short Form Pain Interference 4a v1.0 at each time point will be summarized for each nominal visit and by treatment. Individual item scores are totaled to obtain a raw score, with higher scores indicating more interference. Raw scores can be converted to a T-score.

3.13. Pharmacokinetic/Pharmacodynamic Methods

PK, PD, and PK/PD analysis are the responsibility of Lilly’s PK/PD group.

A summary of tirzepatide concentration-time data will be reported in the CSR. Exposure-response analysis between tirzepatide concentration and safety, pharmacology, and efficacy may be performed using population PK and population PK/PD nonlinear mixed-effects modeling techniques implemented on NONMEM software.

If ADA titers are detected in the immunogenicity samples, the impact of titers on tirzepatide PK and/or PD may be evaluated.

3.14. Safety Analyses

Unless specified otherwise, safety assessments will be based on the SS ([Table GPHR.3.1](#)). All events that occur between the date of first dose of study drug to the date of patient's safety follow-up visit or patient's end of study participation will be included, regardless of the adherence to study drug or availability of the end of treatment liver biopsy. For assessing the benefit and risk profile through 52 weeks, selected safety analyses will be conducted by utilizing safety data from first dose through the date of the 52-week visit.

The statistical assessment of homogeneity of the distribution of categorical safety responses among treatment arms will be conducted using Fisher's exact test, unless specified otherwise.

The mean change from baseline differences among treatments at all scheduled visits will be assessed via an MMRM using REML, unless specified otherwise. The model will include baseline T2DM status (Yes/No), the region (Japan, US including Mexico, and Europe including Israel), treatment group, visit and treatment-by-visit interaction as fixed effects, and baseline value of the safety parameter as a covariate. To model the covariance structure within patients, the unstructured covariance matrix will be used. If this model fails to converge, the covariance structures specified in Section [3.11.2.1](#) will be tested in order.

For selected safety parameters, time-to-first-event analysis via the Cox Proportional-Hazards model may be conducted. Patients without the event will be censored at the end of study participation. For patients experiencing the event, the "time-to-first-event" will be the time (in days) from first dose to first occurrence of the event.

Where necessary, the rate of events will be analyzed using a generalized linear mixed-effects model assuming the number of events follow a negative binomial distribution and with treatment as a fixed effect. The logarithm of days during the active treatment period will be adjusted as an offset to account for possible unequal treatment duration of follow-up between patients.

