# 9.2. Sample Size Determination

Approximately, 196 participants will be randomized to placebo, tirzepatide 5 mg, tirzepatide 10 mg, or tirzepatide 15 mg in a 1:1:1:1 ratio; assuming a 20% dropout rate, this results in approximately 40 completers per arm. Sample size selection is guided by the objective of establishing superiority of each tirzepatide dose to placebo relative to the proportion of participants achieving NASH resolution without worsening of fibrosis at 52 weeks from randomization. The evaluation of superiority to placebo will be conducted for each of the 3 tirzepatide doses at 2-sided significance level of 0.05 using a test of 2 proportions. The tirzepatide group mean response rate is assumed to be 42.5% and the placebo group mean response rate is assumed to be 12.5%. The chosen sample size provides at least 80% power to establish superiority of tirzepatide 5 mg, tirzepatide 10 mg, or tirzepatide 15 mg doses to placebo. No adjustment for multiplicity will be performed.

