## 9.4.4. Safety Analyses

The SS will be used for safety analyses. The overall comparison of tirzepatide doses versus placebo will be reported for these safety analyses. Safety measures will include vital signs, body weight, TEAEs (including SAEs and AEs of special interest), laboratory measures (including ADAs), and ECGs.

Summary statistics will be presented by treatment for the safety measures. Counts and proportions of subjects experiencing AEs will be reported for each treatment group. Fisher's exact test may be used to compare the treatment groups.

Adverse events will be coded from the actual term using the Medical Dictionary for Regulatory Activities (MedDRA) and reported with preferred terms and system organ class.

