2.2. Determination of Sample Size

Sample size selection is guided by the objective of establishing superiority of each tirzepatide dose to placebo relative to the proportion of participants achieving NASH resolution without worsening of fibrosis at 52 weeks from randomization. The evaluation of superiority to placebo will be conducted for each of the 3 tirzepatide doses at 2-sided significance level of 0.05 using a test of 2 proportions. The power is assessed based on the following assumptions:

- the tirzepatide group mean response rate is assumed to be 42.5%
- the placebo group mean response rate is assumed to be 12.5%
- the dropout rate is assumed to be a 20%, and
- 1:1:1:1 randomization.

On the basis of these assumptions, approximately 196 participants will be required to provide at least 80% power to establish superiority of tirzepatide 5-mg, tirzepatide 10-mg, or tirzepatide 15-mg doses to placebo. This results in approximately 40 completers per arm. No adjustment for multiplicity will be performed.

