2.3. Method of Assignment to Treatment

Approximately 196 patients who meet all criteria for enrollment will be randomized to one of the study treatment arms at Visit 3. Assignment to treatment arms will be determined by a computer-generated random sequence using an interactive web response system. Patients will be randomized in a 1:1:1:1 ratio to receive 5-mg tirzepatide, 10-mg tirzepatide, 15-mg tirzepatide, or placebo. Patients will be stratified at randomization based on T2DM status (Yes or No) and the region (Japan, US including Mexico, and Europe including Israel).

3. A Priori Statistical Methods

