3.2. General Considerations

Statistical analysis of this study will be the responsibility of Eli Lilly and Company (Lilly) or its designee. All statistical analyses will be conducted with SAS Version 9.4 or higher unless otherwise stated. Some analyses and summaries described in this analysis plan may not be conducted if not warranted by data (e.g., few events to justify conducting an analysis). Listings of events will be provided in such situations. Additional analyses of the data may be conducted as deemed appropriate without further changes made to the protocol or SAP, even after the primary or final database locks.

Additionally, to avoid potential selection biases, unless stated otherwise, statistical summaries and analyses will be conducted based on randomized study treatment group regardless of the actual treatment received by the patient. Unless otherwise noted, all tests of treatment effects will be conducted at a 2-sided alpha level of 0.05, and the CI will be calculated at 95%, 2-sided. In statistical summaries and analyses, patients will be analyzed as randomized.

For histological, imaging, and TE measurements the last available data during Visit 1 to Visit 3 prior to or within 1 week after the first study drug administration will serve as baseline. For patients who have an eligible historical biopsy within 6 months of Visit 1, the historical biopsy will serve as baseline for histological measures. Unless specified otherwise, the last measurement during Visit 1 to Visit 3 (including unscheduled visits) collected prior to or on the first dose day will serve as baseline. For immunogenicity, data collected up to the first dose time will serve as baseline. For laboratory and ECG, baseline needs to be prior to or within 1 hour after the first dose time. For PROs, data collected at Visit 3, regardless of the timing relative to the first dose, will serve as baseline.

There will be 2 estimands of interest in evaluating the primary and secondary efficacy objectives. The first estimand, the “efficacy” estimand, represents efficacy prior to discontinuation of study drug.

Primary Estimand (efficacy estimand)

The primary clinical question of interest is: What is the treatment difference in NASH resolution without worsening of fibrosis after 52 weeks of treatment assuming all participants who meet the inclusion criteria would have completed the treatment period?

The “efficacy estimand” is described by the following attributes:

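### SAP 3.14 does not carry over the protocol's overall tirzepatide-versus-placebo safety comparison: its categorical default is a four-arm homogeneity test, with no pooled group and no risk difference.

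*SAP*

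**What the plan says.** Protocol 9.4.4 commits to an overall safety result: "The overall comparison of tirzepatide doses versus placebo will be reported for these safety analyses". The same section has adverse-event counts and proportions reported for each group, and makes Fisher's exact test between groups optional. The word pooled does not appear there.

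SAP 3.14 sets the default for categorical safety as "The statistical assessment of homogeneity of the distribution of categorical safety responses among treatment arms", carried out with Fisher's exact test unless a later section says otherwise. The section names no risk difference and no confidence interval for these outcomes, and the summaries that follow are by treatment.

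Three other places bear on the point:

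- **SAP 3.2** says that statistical comparisons will be made between tirzepatide doses and placebo. It also fixes a display order of four columns (5, 10 and 15 mg, then placebo), none of them pooled.
- **SAP 1.4** pools the three doses for the primary and secondary MRE objectives. No safety section does so.
- **Protocol 9.4.1** says that a change of analysis method short of a principal feature is to be described and justified in the SAP or the clinical study report. The SAP mentions no change on this point.

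**The concern.** For most adverse events of special interest, the first question is whether the drug causes more of them than placebo. A homogeneity p-value does not answer it directly. It has no direction, it can be driven by differences between doses, and it comes with no effect size. Whether the protocol's overall comparison means one pooled contrast or each dose against placebo, a four-arm homogeneity test is neither.

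The specific safety rule (homogeneity) and the general rule in SAP 3.2 (dose versus placebo) also leave it unclear which contrast the safety tables will carry. At stake are the size and precision of the drug-versus-placebo difference for uncommon events, where 49 per arm is small and the 147 treated participants would say more.

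**Working it through.** **The plan's own figure.** Protocol 9.2 and SAP 2.2 give rates of 42.5% and 12.5%, two-sided 0.05 and 80% power. With a mean rate of 0.275:

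- n = [1.96 × √(2 × 0.275 × 0.725) + 0.842 × √(0.125 × 0.875 + 0.425 × 0.575)]² / 0.30² = 33.6, so 34 per arm.
- With the continuity correction, n = (33.6/4) × [1 + √(1 + 4/(33.6 × 0.30))]² = 40 per arm.
- With 20% dropout, 40/0.8 = 50 per arm, or 200 in total. The plan has 196, and 196 × 0.8/4 = 39.2 completers per arm.
- Exact Fisher power at 40 per arm is 82.1%.

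So "approximately 196 participants will be required to provide at least 80% power" reproduces. The documents state no power for any safety comparison.

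**Inputs for safety.** Equal allocation of 196 gives 196/4 = 49 per arm and 3 × 49 = 147 on tirzepatide, taking every randomized participant as dosed. SAP 3.2 says that "all tests of treatment effects will be conducted at a 2-sided alpha level of 0.05". The documents give no adverse-event rates for this population, so every rate below is an assumption shown over a range.

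**Power.** All possible outcomes were enumerated exactly. For each total number of events, tables were ranked by their conditional probability, and those with a Fisher p-value of at most 0.05 counted as rejections. The four-arm test is the 2×4 extension of Fisher's test; the pooled test is 2×2, 147 versus 49.

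| Assumed rates (placebo/5/10/15 mg) | Four-arm | Pooled | Pooled minus four-arm (points) |
|---|---|---|---|
| 2/10/10/10% | 31% | 42% | +11 |
| 2/12/12/12% | 46% | 61% | +15 |
| 2/15/15/15% | 67% | 81% | +14 |
| 5/15/15/15% | 33% | 45% | +11 |
| 5/20/20/20% | 62% | 75% | +13 |
| 5/25/25/25% | 85% | 93% | +8 |
| 10/20/20/20% | 24% | 31% | +7 |
| 10/25/25/25% | 48% | 61% | +13 |
| 10/30/30/30% | 73% | 85% | +12 |
| 2/6/12/18% | 70% | 61% | −10 |
| 5/12/20/28% | 82% | 75% | −7 |
| 10/20/30/40% | 90% | 85% | −5 |
| 5/10/15/25% | 71% | 56% | −15 |
| 5/10/20/30% | 89% | 75% | −14 |
| 10/15/20/30% | 58% | 41% | −17 |
| 5/5/5/20% | 67% | 14% | −54 |
| 10/10/10/30% | 75% | 16% | −60 |

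Differences were taken before rounding. With 10% in every arm, the actual type I error is 4.7% (four-arm) and 3.8% (pooled).

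**Precision.**

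- With zero events, the one-sided 95% upper bound is 1 − 0.05^(1/n): 5.9% for n = 49 and 2.0% for n = 147.
- At 5% versus 20%, the 95% half-width of the risk difference is 1.96 × √(0.05 × 0.95/49 + 0.20 × 0.80/n): 12.8 points for one dose (n = 49) and 8.9 points pooled (n = 147).

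**The case against.** The strongest case on the other side is that the plan already suits a dose-finding study, and that pooling could hide harm. Four stronger readings are tempting, and the documents support none of them.

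- **That the homogeneity test is the only safety test.** It is a default. SAP 3.2 plans dose-versus-placebo comparisons. SAP 3.14 allows time-to-event and event-rate models, SAP 3.14.1.5 plans time-to-event analysis of discontinuation due to adverse events, and SAP 3.14.4 compares laboratory shifts between treatments.
- **That the protocol promised a pooled contrast.** Protocol 9.4.4 speaks of doses in the plural and never of pooling. Each dose against placebo is a fair reading too.
- **That real harm will be detected less often.** This holds only if the doses carry similar risk. Protocol 4.3 reports that gastrointestinal events in the earlier Phase 2 study rose with dose, and under that pattern the four-arm test is the stronger one.
- **That pooled tirzepatide should become the stated categorical comparison.** This would put first the contrast least sensitive to harm confined to one dose, in a study meant to inform dose selection.

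It is also fair to say that a reader can add three counts to get the pooled one, so the tighter zero-event bound does not depend on which test is used, and that SAP 3.2 permits further analyses without amendment.

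All of this stands against replacing the planned test. It does not meet the narrower point. The SAP nowhere says how the protocol's overall comparison will be delivered, and it names no effect size or interval for categorical safety. Nor is pooling foreign to the design: under Protocol 6.1 the three active arms follow the same dosing schedule in Weeks 0 to 7, and the 10 and 15 mg arms do so through Week 15, so early events arise under common exposure.

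**Conclusion.** The point holds as a gap between protocol and SAP, and as a cheap improvement. It does not show that the plan is weak at detecting harm. Across the assumed rates, pooling gains about 7 to 15 points of power when risk is equal across doses, loses about 5 to 17 when risk is graded by dose, and loses about 54 to 60 when only 15 mg is affected. The two tests answer different questions, and neither should displace the other.

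The gain in precision is firmer. Adding the pooled group lowers the zero-event upper bound from 5.9% to 2.0%, and at 5% versus 20% it narrows the half-width from 12.8 to 8.9 points. The pooled difference describes the average over doses, so it must be read with the by-dose figures. The power figures and the half-widths rest on assumed event rates, and all figures rest on 49 dosed participants per arm.

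**What to change.** In SAP 3.14:

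1. Add a pooled-tirzepatide column to the tables of TEAEs, SAEs, discontinuations and AESIs, and to the categorical laboratory, vital-sign and ECG tables.
2. State that pooled tirzepatide versus placebo is reported in addition to each dose versus placebo, each with a risk difference and 95% confidence interval.
3. Keep the by-dose columns and the homogeneity test.
4. Say that this is how the overall comparison in Protocol 9.4.4 is delivered, and extend the display order in SAP 3.2 to match.

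The cost is about one sentence and one column, with no new data. The downsides are one more contrast per table in a study without multiplicity adjustment, and a pooled figure that can mask a dose-limited effect if read alone. The retained by-dose results guard against the latter.

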3.14.1. Adverse Events

If applicable, a listing of AEs occurring either before first dose or after the patient's last date of study participation will be provided. The listing will include patient identification including the treatment, site number, event information: AE group ID, event start date, MedDRA SOC, and PT, seriousness, severity, outcome, relationship to study drug, time from first dose of study drug to the event, time from last dose of study drug to the event, and time from end of study participation to the event.

3.14.1.1. Treatment-Emergent Adverse Events

A TEAE is defined as an event that first occurred or worsened in severity after first dose of study drug. The MedDRA LLT will be used in the treatment-emergent derivation. The maximum severity for each LLT during the baseline period including ongoing medical history will be used as baseline severity. For events with a missing severity during the baseline period, it will be treated as “mild” in severity for determining treatment-emergence. Events with a missing severity during the postbaseline period will be treated as “severe” and treatment-emergence will be determined by comparing to baseline severity.

For events occurring on the day of first taking study medication, the CRF-collected information (e.g., treatment-emergent flag, start time of study treatment and event) will be used to determine whether the event was pre- versus post-treatment, if available. If the relevant information is not available, then the events will be counted as post-treatment.

The counts and percentages of participants with TEAEs will be summarized by treatment using MedDRA PT nested within SOC. Events will be ordered by decreasing frequency within SOC. The SOC will be in alphabetical order. For events that are sex-specific, the denominator and computation of the percentage will include only participants from the given sex.

An overview of the number and percentage of participants who experienced a TEAE, SAE, death, discontinued from study treatment or study due to an AE, relationship to study drug, and outcome of the AE will be summarized by treatment.

The counts and percentages of patients with TEAEs by maximum severity will be summarized by treatment using MedDRA PT. For each participant and TEAE, the maximum severity for the MedDRA PT is the maximum postbaseline severity observed from all associated LLTs mapping to the MedDRA PT. The maximum severity will be determined based on the nonmissing severities. If all severities are missing for the defined postbaseline period of interest, it will show as missing in the table.

3.14.1.2. Common Adverse Events

The counts and percentages of participants with TEAEs, overall and common (common TEAEs occurred in $\geq 1.0\%$ of participants before rounding), will be summarized by treatment using MedDRA PT. Events will be ordered by decreasing frequency.

3.14.1.3. Deaths

A listing of all deaths during the study will be provided. The listing will include participant identification including the treatment, site number, date of death, age at the time of enrollment, sex, MedDRA PT, associated AE group identification, time from last dose of study drug to death (if participant had discontinued study drug), investigator-reported cause of death, and CEC-adjudicated cause of death.

3.14.1.4. Other Serious Adverse Events

The counts and percentages of participants who experienced an SAE (including deaths and SAEs temporally associated or preceding deaths) during the postbaseline period will be summarized by treatment using MedDRA PT nested within SOC. Events will be ordered by decreasing frequency within SOC. The SOC will be in alphabetical order.

A listing of all SAEs will be provided. The listing will include, but not be limited to, treatment, participant identification including the site number, date of event, age at the time of enrollment, sex, AE group identification, MedDRA SOC and PT, severity, action taken, outcome, relationship to study drug, time from first dose of study drug to the event, and event duration.

3.14.1.5. Discontinuation Due to Adverse Events

The counts and percentages of participants who discontinued from study treatment or study due to an AE during the postbaseline period may be summarized by treatment group using MedDRA PT nested within SOC. Events will be ordered by decreasing frequency within SOC. In case of discontinuation from study treatment, a time-to-event analysis will be conducted by treatment on time to study drug discontinuation as well as on time to study drug discontinuation due to an AE.

